7.3.2.2. AEs and SAEs by System Organ Class (SOC) and Preferred Term (PT)

The number of TEAEs, and the number and percentage of patients with events will be presented by SOC and PT. Patients will be counted once in each SOC and PT. Percentages will be based on the total number of treated patients (safety set). SOC's will be listed in descending order of frequency of occurrence. SAEs will be summarized similarly.

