6.1.2. Secondary Objectives

The secondary objectives of the study are to assess the following:

1. To characterize the safety and tolerability of ALXN1210 in this patient population
2. To evaluate the efficacy of ALXN1210 by the following additional measures:
 - a. Dialysis requirement status
 - b. Time to Complete TMA Response
 - c. Complete TMA Response status over time
 - d. Observed value and change from baseline in estimated glomerular filtration rate (eGFR)
 - e. Chronic kidney disease (CKD) stage, as evaluated by eGFR at select target days and classified as improved, stable (no change), or worsened compared to baseline
 - f. Observed value and change from baseline in hematologic parameters (platelets, LDH, hemoglobin)
 - g. Increase in hemoglobin of ≥ 20 g/L from baseline, observed at 2 separate assessments obtained at least 4 weeks (28 days) apart, and any measurement in between
 - h. Change from baseline in quality of life (QoL), as measured by EuroQol 5 dimensions 3 level (EQ-5D-3L; all patients), Functional Assessment of Chronic Therapy (FACIT) Fatigue version 4 (patients ≥ 18 years of age), and Pediatric FACIT Fatigue (patients < 18 years of age) questionnaires
 - i. TMA parameters in patients who discontinue treatment but remain in the study
3. To characterize the PK/pharmacodynamics (PD) of ALXN1210 by the following measures:
 - a. Changes in serum ALXN1210 concentration over time
 - b. Changes in free C5 concentrations over time
 - c. Changes in free C5 and ALXN1210 concentration in patients who discontinue treatment but remain in the study
4. To evaluate the long-term safety and efficacy of ALXN1210

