7.1. Summary of Study Design

Study ALXN1210-aHUS-311 is a Phase 3, open-label, single arm, multicenter study to evaluate the safety and efficacy of ALXN1210 administered by intravenous (IV) infusion to adolescent (12 to < 18 years of age) and adult (≥ 18 years of age) patients with aHUS. The study will enroll approximately 55 patients to receive ALXN1210. All patients must be naïve to complement inhibitor treatment and include at least 6 and up to 10 adolescent (12 to < 18 years of age at Screening) patients and at least 10 and up to 25 patients with prior kidney transplants. A minimum of 30 patients who meet all laboratory criteria for TMA (platelet count of < 150,000 per microliter, LDH $\geq 1.5 \times$ upper limit of normal (ULN), hemoglobin \leq lower limit of normal (LLN), and serum creatinine level \geq ULN) as determined by the central laboratory at Day 1, will be enrolled.

The study consists of an up to 7 day Screening Period, a 26-week Initial Evaluation Period, and an Extension Period until the product is registered or approved (in accordance with country-specific regulations) or for up to 4.5 years, whichever occurs first. Dosages are based on the patient's body weight recorded at the last visit or more recently (Table 6). Patients will receive a loading dose of ALXN1210 IV (2400 mg for patients weighing ≥ 40 to < 60 kg, 2700 mg for patients weighing ≥ 60 to < 100 kg, 3000 mg for patients weighing ≥ 100 kg) on Day 1, followed by maintenance doses of ALXN1210 IV (3000 mg for patients weighing ≥ 40 to < 60 kg, 3300 mg for patients weighing ≥ 60 to < 100 kg, 3600 mg for patients weighing ≥ 100 kg) on Day 15 and once every 8 weeks (q8w) thereafter for a total of 26 weeks of treatment in the Initial Evaluation Period followed by maintenance doses q8w in the Extension Period (Figure 1). The end of trial is defined as the last patient's last visit.

Figure 1 illustrates the study design.

Figure 1: Study Design Schematic for Clinical Protocol ALXN1210-aHUS-311

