4. DESCRIPTION OF THE PROTOCOL

ALXN1210-aHUS-311 is a Phase 3, single arm, multicenter study to evaluate the safety and efficacy of ALXN1210 administered by intravenous (IV) infusion to adolescent (12 to < 18 years of age) and adult (≥ 18 years of age) patients with atypical hemolytic uremic syndrome (aHUS). All patients must be naïve to complement inhibitor treatment; at least 6 and up to 10 adolescent (12 to < 18 years of age at Screening) patients and at least 10 and up to 25 patients with prior kidney transplants will be included.

The study consists of an up to 7 day Screening Period, a 26-week Initial Evaluation Period, and an Extension Period of up to 2 years. Dosages are based on the patient’s last recorded study visit body weight. Patients will receive a loading dose of ALXN1210 IV (2400 mg for patients weighing ≥ 40 to < 60 kg, 2700 mg for patients weighing ≥ 60 to < 100 kg, 3000 mg for patients weighing ≥ 100 kg) on Day 1, followed by maintenance doses of ALXN1210 IV (3000 mg for patients weighing ≥ 40 to < 60 kg, 3300 mg for patients weighing ≥ 60 to < 100 kg, 3600 mg for patients weighing ≥ 100 kg) on Day 15 and once every 8 weeks (q8w) thereafter for a total of 26 weeks of treatment. After the Initial Evaluation Period, patients will enter an Extension Period and receive ALXN1210 until the product is registered or approved (in accordance with country specific regulations) or for up to 2 years, whichever occurs first. The end of trial is defined as the last patient’s last visit.

Figure 1: Study Design Schematic for Clinical Protocol ALXN1210-aHUS-311 illustrates the study design.

Figure 1: Study Design Schematic for Clinical Protocol ALXN1210-aHUS-311

The primary objective of the study is to assess the efficacy of ALXN1210 in patients with aHUS to inhibit complement-mediated thrombotic microangiopathy (TMA) as characterized by thrombocytopenia, hemolysis, and renal impairment, as determined by Complete TMA Response following treatment.

Secondary objectives of the study include the following:

1. To characterize the safety and tolerability of ALXN1210 in this patient population
2. To evaluate the efficacy of ALXN1210 by the following additional measures:

- a. Dialysis requirement status
 - b. Time to Complete TMA Response
 - c. Complete TMA Response status over time
 - d. Observed value and change from baseline in estimated glomerular filtration rate (eGFR)

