7.3.1. Study Duration, Treatment Compliance, and Exposure

Two summary tables of the extent of exposure to ALXN1210 will be presented. The duration on treatment (in weeks), the number of infusions, and the total dose (in mg) through the first 26 weeks (ie, Initial Evaluation Period) will be summarized using descriptive statistics. In addition, a similar table will be produced for exposure throughout the entire study.

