7.3.2.1. Overall Summary of Adverse Events

An overall summary of AEs and SAEs will be presented. The number of events (n), and number and percentage of patients with events (n, %) will be shown for the following event subcategories:

Table 4: Adverse Events (AEs) and Serious AEs

Relationship	Severity: Toxicity Grade
Related AEs (Possibly, Probably, or Definitely Related)	Grade 1
Not Related AEs (Not Related or Unlikely Related)	Grade 2
	Grade 3
	Grade 4
	Grade 5

Fatal TEAEs, TEAEs resulting in study treatment discontinuation, TEAEs resulting in withdrawal from the study, and TEAEs that start during study drug administration will also be included in this overall summary. These statistics will be prepared separately for all AEs and SAEs.

Detailed listings of all AEs, SAEs, and related AEs, will be presented. These listings will include severity and relationship to treatment, as well as action taken regarding study treatment, other action taken, and AE outcome.

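### The entire-study adverse-event tables give counts and crude percentages without patient-time, although follow-up may differ up to tenfold (Protocol) or fivefold (SAP), so the percentages mix risk with time on study

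*SAP*

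**What the plan says.** - **Adverse-event tables.** SAP 7.3.2.1, the overall summary: "The number of events (n), and number and percentage of patients with events (n, %) will be shown". SAP 7.3.2.2: "The number of TEAEs, and the number and percentage of patients with events will be presented by SOC and PT", with the denominator "Percentages will be based on the total number of treated patients (safety set". SAP 7.3.2.3 and 7.3.2.4 use the same format by relationship and severity. SAP 7.3.2.5 adds a table and a listing for meningococcal infection. Protocol 15.9.1 plans incidence summaries of the same kind.
- **Exposure.** SAP 7.3.1 summarizes "The duration on treatment (in weeks), the number of infusions, and the total dose (in mg) through the first 26 weeks", and adds that "a similar table will be produced for exposure throughout the entire study". SAP 7.3 splits safety output by age category, with exceptions only for immunogenicity and physical examination, so exposure is split too.
- **Length of follow-up.** Protocol 7.1: "an Extension Period until the product is registered or approved (in accordance with country-specific regulations) or for up to 4.5 years, whichever occurs first". SAP 4 also ends treatment at approval, but otherwise "or for up to 2 years, whichever occurs first".
- **Aim.** Protocol 6.1.2 lists as a secondary objective "To evaluate the long-term safety and efficacy of ALXN1210".

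Neither document plans patient-years, exposure-adjusted rates or time to first event. The adverse-event sections also do not say whether the tables for the 26-week report stop at Day 183.

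**The concern.** How long a patient is observed depends partly on when the product is approved in that patient's country, which has nothing to do with that patient's risk of an adverse event. A patient who leaves soon after Day 183 and one who stays to Day 1863 each count as one in the denominator, yet the second has far longer in which to have an event. The percentage in the final report is an average over whatever mix of follow-up times occurred.

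Three readings suffer. The 26-week and final reports cannot be set side by side. The age columns cannot be compared if follow-up differs between them, and with only 6 to 10 adolescents planned a few early exits could cause that. Comparison with other studies is also weakened, and Protocol 7.2 expects the results to be viewed in the context of the eculizumab studies. For meningococcal infection, the only targeted event in Protocol 11.7.1, a count of zero means little without the patient-time behind it.

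**Working it through.** **1. Follow-up range.** Visit days come from Protocol 7.3, Tables 1 to 3. The schedule reproduces:

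- Day 183 = 1 + 26 × 7.
- Day 911 = 183 + 13 × 56. The extension to this day is 728/365.25 = 1.99 years (SAP: 2).
- Day 1863 = 183 + 30 × 56. The extension to this day is 1680/365.25 = 4.60 years (Protocol: 4.5).

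Follow-up from Day 1:

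- Day 183: 182/365.25 = 0.50 years.
- Day 911: 910/365.25 = 2.49 years.
- Day 1863: 1862/365.25 = 5.10 years.

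The ratios are 1862/182 = 10.2 under the Protocol and 910/182 = 5.0 under the SAP. Adding 56 days at both ends, for a window that closes 56 days after the last dose, gives 1918/238 = 8.1 and 966/238 = 4.1. These ranges are for patients who complete 26 weeks; early withdrawals widen them.

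**2. Effect on a crude percentage.** The documents give no adverse-event rates, so a constant first-event rate λ is assumed and varied. The expected percentage is 1 − exp(−λt).

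| λ per year | 26 weeks | Day 911 | Day 1863 | Day 1863 ÷ 26 weeks |
|---|---|---|---|---|
| 0.02 | 1.0% | 4.9% | 9.7% | 9.8 |
| 0.05 | 2.5% | 11.7% | 22.5% | 9.1 |
| 0.1 | 4.9% | 22.1% | 39.9% | 8.2 |
| 0.5 | 22.1% | 71.2% | 92.2% | 4.2 |
| 1.0 | 39.2% | 91.7% | 99.4% | 2.5 |

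Risk per year is the same along each row. For a mixed cohort at λ = 0.1, if 25%, 50% or 75% of patients stay to Day 1863 and the rest leave at Day 183, the table shows 13.6%, 22.4% or 31.2%.

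**3. A zero count in 55 patients.** The exact one-sided 95% upper bound on the proportion is 1 − 0.05^(1/55) = 5.3% (rule of three: 3/55 = 5.5%). It does not depend on follow-up. The bound on the rate is −ln(0.05)/patient-years = 2.996/patient-years:

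| All 55 followed to | Patient-years | Upper bound per 100 patient-years |
|---|---|---|
| Day 183 | 55 × 182/365.25 = 27 | 10.9 |
| Day 911 | 55 × 910/365.25 = 137 | 2.2 |
| Day 1863 | 55 × 1862/365.25 = 280 | 1.1 |

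**4. Can a reader rebuild the rate?** Only roughly. The number of patients times mean duration on treatment gives a total, and events divided by that total gives an all-events rate. Two things are missing. First-event rates cannot be recovered, because time to first event is not tabulated. The denominator may also not match the numerator. The SAP (5.2.1, 7.3.2, 9.4.6) puts no upper time limit on a treatment-emergent event, Protocol 15.9.1 closes the window 56 days after the last dose, and SAP 4.1 lists no changes from the Protocol. Under Protocol 8.3.2 patients may stay on study off drug, and under Protocol 15.1 adverse events after retreatment are pooled back in. Duration on treatment need not equal time at risk under either definition.

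**The case against.** The strongest reply is that the plan supplies more than percentages. Event counts are tabulated, exposure is summarized for the whole study and by age category, and a zero-event bound needs only total exposure. That stands: a reader might infer that long-term safety will appear only as percentages, or that a zero meningococcal count could not be interpreted, and the SAP does not support either reading. It does not follow that a hand calculation is enough, because of the mismatch in step 4 and the lack of any confidence interval.

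Further points that stand:

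- In a single-arm study unequal follow-up cannot bias a contrast between arms, and no formal safety comparison is planned. The SAP's own reference to eculizumab results sits in the primary efficacy section (7.2.1).
- Tenfold is the Protocol's range. The SAP still describes a 2-year extension (SAP 4 and 4.3), and Protocol 15.13 also places the second analysis at the end of 2 years.
- Both ranges are limits. No approval dates or actual follow-up times are given, and nothing shows that follow-up differs by age.
- A constant rate is unproven in patients enrolled during acute disease. If events cluster early, a pooled long-term rate would dilute them.
- Adding rates to every row by organ class, relationship and severity in about 55 patients would be out of proportion.

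**Conclusion.** The concern holds as a reporting gap that should be closed. Because the extension ends partly by country approval, a percentage of the Safety Set does not describe long-term risk unless patient-time is shown with it. A reader might go further and infer that the percentages measure time on study instead of risk. They do not: they mix the two, and the 2.5-fold to 9.8-fold spread is an upper illustration, comparing everyone at Day 1863 with everyone at 26 weeks. It rests on assumed constant rates of 0.02 to 1.0 per year; the patient-year bounds rest on 55 patients all followed to the stated day.

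The primary analysis is untouched and no decision rule depends on these tables. What is affected is the secondary long-term safety objective, and above all what a low or zero meningococcal count can be said to exclude.

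**What to change.** 1. **Reconcile first.** State one treatment-emergent window (the SAP leaves it open; the Protocol closes it at 56 days after the last dose) and one extension length (4.5 years in the Protocol, 2 years in the SAP), including the timing of the final analysis in SAP 4.3 and Protocol 15.13.
2. **Add rates where they matter.** For the entire-study analysis, add total patient-years at risk and events per 100 patient-years with a 95% CI to the overall summary, the SAE tables and the meningococcal table, overall and by age group. Take the at-risk time that matches the reconciled window, not duration on treatment. Use first-event rates, or a CI that allows for repeat events within a patient, since a simple Poisson interval for all events may be too narrow.
3. **Tabulate the fixed 26-week period separately**, cut at the end of the Initial Evaluation Period, so that early clustering stays visible and the tables have nearly equal follow-up.

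The cost is one derived at-risk-time variable, a few columns in selected tables and one further set of 26-week tables where they are not already produced. No new data are collected. The remaining weakness is that a pooled rate summarizes well only if the hazard is roughly constant, which is why item 3 belongs with item 2.

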7.3.2.3. AEs and SAEs by SOC, PT, and Relationship

The number of TEAEs, and the number and percentage of patients with events will be presented by SOC and PT as described above by relationship (related, not related). If a patient has more than one occurrence of an AE, the strongest relationship to study treatment will be used in the relationship to treatment summary table. SAEs will be summarized similarly.

7.3.2.4. AEs and SAEs by SOC, PT, and Severity

The number of TEAEs, and the number and percentage of patients with events will be presented by SOC and PT as described above by severity (using toxicity grade). If a patient has more than one occurrence of an AE, the most severe occurrence of the AE will be used in the severity summary table. SAEs will be summarized similarly.

7.3.2.5. Deaths, Other SAEs, and Other Significant Adverse Events

Individual listings will be presented for AEs leading to study treatment discontinuation, AEs leading to withdrawal from the study, AEs starting during study drug administration, and fatal AEs.

In addition, a summary table and a listing of AEs related to meningococcal infections will be provided. See [Section 9.4.7](#) for a list of AE preferred terms that will be considered for these summaries of meningococcal infections.

7.3.3. Other Safety

7.3.3.1. Analyses for Laboratory Tests

Observed values and changes from baseline in clinical chemistry, hematology, and urinalysis results will be summarized descriptively at baseline, and at each postbaseline time point. For laboratory results that can be classified as normal, low, or high based on normal range values, shifts from baseline in classification will be summarized for all study visits.

All data will be presented in listings, and a specific listing of abnormal results will be provided. For analysis purposes, laboratory results based upon standardized units will be used.

7.3.3.2. Vital Signs

Observed values as well as changes from baseline in body weight and vital signs (blood pressure, heart rate, respiratory rate, pulse oxymetry, and temperature) at each time assessment will be summarized descriptively. A listing of vital signs data will be presented by patient, vital sign, and visit.

7.3.3.3. Other Safety Parameters of Special Interest

7.3.3.3.1. Electrocardiograms

By-patient data listings of ECG parameters will be provided. Electrocardiograms will be evaluated and summarized as normal, abnormal not clinically significant, or abnormal clinically significant. A shift from baseline to worst on-study ECG table will be presented for ECG results. Observed values and change from baseline in ECG intervals (PR, RR, QT, and QTc) will be summarized descriptively at baseline and each postbaseline time point. QT interval will be corrected for heart rate using Friderica's formula (QTcF).

7.3.3.3.2. Immunogenicity

The number and percentage of patients with positive titers for ADAs to ALXN1210 and different titer categories will be summarized over time. The proportion of patients ever positive and the proportion of patients always negative will also be summarized.

7.3.3.3.3. Physical Exam

Physical Exam parameters collected include General Appearance, Skin, HEENT (head, ears, eyes, nose and throat), Neck, Lymph Nodes, Chest, Heart, Abdominal Cavity, Limbs, Musculoskeletal, and Central Nervous System. Each parameter is assessed by the Investigator as Normal, Abnormal, or Not Examined. A listing of Physical Exam results will be presented by patient, Physical Exam parameter, and visit.

9. APPENDICES

9.1. Protocol Schedule of Events

See protocol section 7.3.

9.2. Changes from Analyses Specified in the Previous Version of the SAP

Not applicable.

9.3. Sample Size, Power, and Randomization

Approximately 55 patients will be enrolled in this study in order to yield at least 50 evaluable patients by Day 183. This sample size is deemed appropriate to provide complete safety information and the necessary precision level for the planned estimation. Assuming a proportion of Complete TMA response of 65%, 50 patients would yield a 95% confidence interval for the proportion of response with a half-width of approximately 15%.

The sample size was increased to 55 patients to account for a potential 10% drop-out rate, thus yielding a total planned sample size of 55 patients.

9.4. Technical Specifications for Derived Variables

9.4.1. Age

Table 5: Age and Reference Date

AGE	REFERENCE DATE
• Age at Enrollment	• Date of Informed Consent Form Signing
• Age at First Symptoms	• Date of First Symptoms
• Age at First Infusion	• Date of First Infusion

9.4.2. Definition of Baseline Values

For the analysis, the baseline value is defined as the average of the values from the assessments performed prior to the first study drug infusion (these can include results from Screening and the Day 1 visit).

When a patient is on dialysis at baseline, then the first valid creatinine value to be used as the baseline value will be the first assessment ≥ 6 days post-dialysis. If a patient is on dialysis during the entire 26 week Initial Evaluation Period, then the baseline creatinine will not be calculated.

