7.2.2.5. CKD Stage

CKD stage will be summarized over time by presenting the number and proportion of patients that improved (excluding those with Stage 1 at baseline as they cannot improve), worsened (excluding those with Stage 5 at baseline as they cannot worsen), and stayed the same compared to CKD stage at baseline. Stage 5 will be considered the worst category, while stage 1 will be considered the best category (see [Section 9.4.11](#) for details). A 2-sided 95% CI for each proportion will be provided. The CIs will be based on exact confidence limits using the Clopper-Pearson method. This summary will be repeated by the kidney transplant status at enrollment.

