9.4.3. Change from Baseline

Change from baseline will be calculated as the baseline value subtracted from the value at a particular time point. If one of the values is missing and there are no pre-specified missing value imputation rules (see [Section 7.2.1.1](#)), then a change from baseline will not be calculated.

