9.4.9. Serum Creatinine and eGFR

Serum creatinine measurements are not reliable with concurrent dialysis. Therefore, all serum creatinine values obtained while a patient is on dialysis will be excluded from all analyses. Estimated Glomerular Filtration Rate (eGFR) will be imputed with a value of 10 (in mL/min/1.73 m²) while a patient is on dialysis. A patient will be considered on dialysis from the first day of dialysis through 5 days after the end of dialysis.

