9.4.11. Assignment of CKD Stage

Chronic kidney disease (CKD) stage will be classified based on the National Kidney Foundation Chronic Kidney Disease Stage as follows:

Table 6: Stages of Chronic Kidney Disease

Stage	Description	eGFR (mL/min/1.73 m ²)
1	Normal or High	≥90
2	Mildly Decreased	60-89
3a	Mildly to Moderately Decreased	45-59
3b	Moderately to Severely Decreased	30-45
4	Severely Decreased	15-29
5	Kidney failure	< 15 (or dialysis)

Note: In the absence of evidence of kidney damage, neither stage 1 nor 2 fulfill the criteria for CKD
 Source: [KDIGO 2012 Clinical Practice Guideline for the Evaluation and Management of Chronic Kidney Disease](#). 2013. 3: 19-62.

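### When dialysis starts or stops around Screening, the SAP's baseline eGFR averages the imputed value 10 with a measured value, which biases eGFR change and can distort CKD stage shifts for those patients

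*SAP*

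**What the plan says.** SAP 9.4.2 gives one general rule: "the baseline value is defined as the average of the values from the assessments performed prior to the first study drug infusion". The same section carves out dialysis for creatinine alone: for a patient on dialysis at baseline, "the first valid creatinine value to be used as the baseline value will be the first assessment ≥ 6 days post-dialysis". It has no matching sentence for eGFR or CKD stage.

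SAP 9.4.9 says that eGFR "will be imputed with a value of 10 (in mL/min/1.73 m²) while a patient is on dialysis", and defines that state: "A patient will be considered on dialysis from the first day of dialysis through 5 days after the end of dialysis". It places no postbaseline limit on the imputation. The next section, 9.4.10, does limit its transfusion rule to postbaseline values.

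SAP 9.4.3 fixes the arithmetic: "Change from baseline will be calculated as the baseline value subtracted from the value at a particular time point". In Table 6 (SAP 9.4.11) the Stage 5 entry reads "< 15 (or dialysis", closing its bracket there. SAP 7.2.2.5 counts patients who "worsened (excluding those with Stage 5 at baseline as they cannot worsen", again with the bracket closed at that point.

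Protocol 15.12.1 has a different baseline rule: Day 1, with Screening used only when Day 1 is missing. SAP 4.1 lists no changes from the protocol's analyses.

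**The concern.** Under Protocol 8.1 (criterion 2c) patients who need dialysis for acute kidney injury can enrol, and under 8.2 (criterion 18) those on chronic dialysis cannot. Dialysis at entry is therefore acute and may start or stop close to first dose. Protocol Table 1 schedules chemistry at both Screening and Day 1, and Protocol 11.4.3 has eGFR calculated whenever chemistry is drawn, so two pre-dose eGFR values are the normal case. SAP section 4 says "The study consists of an up to 7 day Screening Period", so there is time for status to change between the two samples.

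When it does, one of the two numbers is a placeholder for kidney failure and the other is a measurement. Their mean describes neither state. Part of a decline or recovery that happened before first dose is then recorded as change after it. The outputs at stake are eGFR change from baseline (with the mixed model for repeated measures in SAP 7.2.2.4, where baseline eGFR is also the covariate) and the CKD stage shifts in SAP 7.2.2.5.

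**Working it through.** The plan states no figure that depends on this rule, so there is nothing to reproduce first. The check applies the SAP's own rules.

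**Inputs.** Baseline is the mean of pre-dose values (SAP 9.4.2). An on-dialysis eGFR is 10 (SAP 9.4.9). Change is visit minus baseline (SAP 9.4.3). Stages are those of Table 6. One value each at Screening and Day 1 is assumed. The measured eGFR values below are illustrative, because the documents give none.

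**Start case: dialysis begins after the Screening sample and before Day 1.** With Screening eGFR S, baseline = (S + 10)/2, and change while dialysis continues = 10 - (S + 10)/2 = -(S - 10)/2.

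| S | Baseline | Stage from averaged eGFR | Change on continued dialysis |
|---|---|---|---|
| 12 | 11 | 5 | -1 |
| 20 | 15 | 4 | -5 |
| 24 | 17 | 4 | -7 |
| 30 | 20 | 4 | -10 |
| 50 | 30 | 3b | -20 |

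Compared with a baseline of 10, the shift is the same at every later visit, including visits after recovery. The averaged value reaches Stage 4 when (S + 10)/2 ≥ 15, that is S ≥ 20. With three pre-dose values the threshold moves: (2S + 10)/3 ≥ 15 gives S ≥ 17.5, and (S + 20)/3 ≥ 15 gives S ≥ 25.

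**Stop case: Screening sample on dialysis by the 9.4.9 definition, Day 1 off it.** With Day 1 eGFR D, baseline = (10 + D)/2, and change if nothing moves afterwards = (D - 10)/2.

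| D | Baseline | Stage at baseline | Stage if unchanged | Change if unchanged |
|---|---|---|---|---|
| 15 | 12.5 | 5 | 4 (improved) | +2.5 |
| 22 | 16 | 4 | 4 (same) | +6 |
| 30 | 20 | 4 | 3b (improved) | +10 |
| 40 | 25 | 4 | 3b (improved) | +15 |

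On-dialysis creatinine is excluded, so this patient's creatinine baseline is the Day 1 value alone, while the eGFR baseline is not.

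**When the stop case can arise.** There is no Day 0. Dialysis ending on Day -6 puts Day 1 six days later, off dialysis; ending on Day -5 puts Day 1 five days later, still imputed as 10. So dialysis must end on Day -6 or earlier. At the other end, dialysis ending on Day -12 keeps Day -7 inside the five-day tail (-12 + 5 = -7). End days from about -12 to -6 can produce the mixture, depending on when the Screening sample was drawn.

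**CKD stage in the start case.** With S ≥ 20 the patient fits two rows of Table 6: Stage 4 or better by averaged eGFR, and Stage 5 by dialysis. If averaged eGFR governs, continued dialysis is counted as worsened. If dialysis status governs, the patient is Stage 5 and drops out of that count. The SAP does not say which.

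**Against the protocol rule.** Protocol 15.12.1 gives baseline 10 in the start case and D in the stop case, so the spurious change is 10 - 10 = 0 and D - D = 0.

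**Effect on a group mean.** In a raw mean over 55 patients, one start-case patient with S = 24 contributes -7/55 = -0.13 mL/min/1.73 m².

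**The case against.** The strongest objection concerns CKD stage. A reader might infer that the plan scores a patient already on dialysis at first dose as worsening. The documents do not support that as a settled result. Table 6 makes dialysis sufficient for Stage 5 whatever the eGFR. SAP 7.2.2.3 ties being on dialysis at baseline to the 5 days before treatment starts. Read together, these make the patient Stage 5 and remove them from the worsened count. The false worsening needs the other reading, so what stands is a missing order of precedence. The dialysis summary in SAP 7.2.2.1 places this patient correctly either way.

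A reader might also want a rate of false worsening. The documents give no number starting dialysis during Screening, no eGFR distribution and no baseline stage counts, so any such percentage would be invented.

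It can further be said that averaging Screening and Day 1 was deliberate (SAP 4.2.1 says so), that any average of a changing quantity blurs it, that the start-case error makes results look worse rather than better, and that creatinine and eGFR baselines already differ by design for patients on dialysis at baseline. All of that is fair. It does not rescue the eGFR change: averaging two measurements reduces noise, but averaging a measurement with a fixed placeholder does not, and the result follows from 9.4.2, 9.4.3 and 9.4.9 however Table 6 is read. The stop case, moreover, errs in the favourable direction.

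**Conclusion.** The point holds as a narrow error in secondary endpoints. For a patient whose dialysis status differs between the two pre-dose samples, eGFR change is off by half the distance between the measured value and 10: downward if dialysis started, upward if it stopped. In the stop case the CKD stage can also be credited with an improvement that preceded treatment. In the start case, with Screening eGFR of at least 20, baseline stage is ambiguous rather than plainly wrong.

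This rests on a literal reading of SAP 9.4.2 and 9.4.9, and the sizes assume one value at each of Screening and Day 1. How many patients are affected cannot be found in the documents. It is probably few, and the effect on mean eGFR is probably small, but stage shifts are counts in a trial of about 55. The primary endpoint is not affected: it uses creatinine, which has its own dialysis rule and excludes on-dialysis values. The trial is an estimation study, so no formal test depends on this.

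**What to change.** Add to SAP 9.4.2: a patient on dialysis at first dose, by the 9.4.9 definition, has baseline eGFR 10 and baseline CKD Stage 5, with no averaging; for every other patient, only pre-dose eGFR values obtained off dialysis are averaged. This removes the spurious change in both cases and settles which row of Table 6 governs at baseline.

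Separately, reconcile the averaged baseline with Protocol 15.12.1. Either adopt the Day 1 rule, or list the averaging in SAP 4.1 as a change from the protocol with its reason.

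The cost is one or two sentences in 9.4.2, an entry in 4.1 if the averaging is kept, and a small programming change. No new data are needed.
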